## 8.2. Treatment Compliance

The study drug compliance (%) will be calculated as:

- Overall Compliance (%) = [total dose exposed (mg) / total dose intended (mg)] x 100
- Compliance (%) on the CS = [Total dose exposed (mg) on the CS / total dose intended (mg) on the CS] x 100
- Compliance (%) on the IS = [Total dose exposed (mg) on the IS / total dose intended (mg) on the IS] x 100

For subjects on study drug at the time of the ORR analysis, the data cut-off (DCO) date will be used to calculate compliance.

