For subjects who experience hematologic toxicity; diarrhea/colitis, cutaneous reactions (including rash and mucositis), AST/ALT elevation, or non-infectious pneumonitis (NIP); or other toxicities, refer to ME-401 toxicity management (Table 4) and modified dosing schedules in [Section 5.3.1](#). Study treatment interruption is acceptable due to observed adverse reactions, and is allowed for up to 6 continuous weeks from drug interruption. Once a subject has recovered from a toxicity, treatment may be resumed beginning at Day 1 of the subsequent cycle of therapy according to the toxicity management indicated in [Table 4](#).

Study drug administration, study visits, and protocol-mandated assessments are conducted in 28-day cycles. Subject participation in the study is expected to be approximately 3–4 years, including 28 days for screening, 18 months of dosing with study drug, and up to 3 years of follow-up for survival after discontinuation of study drug. This is an estimated average duration of subject participation; actual duration may be shorter or longer based on disease response, tolerability to therapy, and duration of the long-term follow-up period.

Disease/response assessments utilizing diagnosis quality scans (CT scan with contrast, diagnostic quality PET/CT scan) will be initially performed at screening, after 4 months and 12 months on therapy, and at any time to confirm CR. Once a CR has been documented, F-fluorodeoxyglucose (FDG)-PET scan is no longer required to monitor disease response and a CT scan is an appropriate imaging test. CT scans will be performed at all other protocol

prespecified timepoints for disease/response assessment. The disease/response assessment will be performed every 2 months ( $\pm 7$  days) for the first 6 months on study, every 3 months ( $\pm 7$  days) during the following 12 months, and every 6 months ( $\pm 14$  days) thereafter.

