### 5.3.1. Modified Dosing Schedules

Modification of the dosing schedule and dosing interruptions are utilized for toxicity management in this study. For subjects who experience toxicity during the first 2 cycles while receiving daily therapy with ME-401, dose interruption followed by a switch to intermittent schedule daily dosing for the first 7 days of every 28-day cycle is allowed. Subjects who experience toxicities on the IS will be managed by the instructions for management of potential drug-related toxicity in [Table 4](#), which may include dose interruption or permanent discontinuation of ME-401. All treatment interruptions (including any missed doses, treatment delays) and discontinuations and their reasons are to be recorded in the electronic case report form (eCRF). Interrupted treatment is resumed on the IS after subjects recover to the grade specified in the table (subjects who permanently discontinue ME-401 dosing will proceed to the EOT/30-Day Safety Follow-up visit). Subjects on the IS who recover within the same treatment cycle, will complete the planned days off, and resume treatment on Day 1 of the next planned cycle.

Subjects who interrupt study drug dosing for  $>6$  continuous weeks will have ME-401 permanently discontinued unless restarting ME-401 is authorized by the study Medical Monitor. Consultation with the Sponsor's Medical Monitor or designee is recommended before treatment interruption or discontinuation due to any reason.

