### **8.1. Extent of Exposure**

Exposure to ME-401 will be evaluated by duration of study drug exposure (months), actual dose intensity, and relative dose intensity for the safety population.

Descriptive statistics will be presented for continuous exposure variables: duration of exposure, actual dose intensity, and relative dose intensity. The number and percentage of subjects with dose schedule modified or dose interrupted due to AE or progressive disease will be summarized. The number and percentage of subjects with dose missed will be summarized by

reason. For subjects on study drug at the time of the ORR analysis, the data cut-off (DCO) date will be used to calculate exposure.

- Duration of exposure (months) = (Date of last non-zero dose – Date of first non-zero dose +1) /30.4375.
- Duration of exposure on the CS (months)
  - = (Date of last non-zero CS dose – Date of first non-zero CS dose +1) /30.4375 for subjects who never switched dosing regimen; or
  - = sum of (Date of last non-zero CS dose – Date of first non-zero CS dose +1) /30.4375 from each CS dosing interval for subjects who switched dosing regimens; date of first or last CS dose can be derived based on the switching date.
- Duration of exposure on the IS (months)
  - = (Date of last zero/non-zero IS dose – Date of first non-zero IS dose +1) /30.4375
- Actual total dose exposed (mg) is defined as the sum of ‘total mg’ of study drug received.
- Total dose intended (mg) is defined as the sum of ‘total mg’ of study drug planned.
  - Total dose intended for the CS is estimated to be 60 mg x Duration of exposure on the CS (months) x 30.4375
  - Total dose intended for the IS is estimated to be (60 mg /4) x Duration of exposure on the IS (months) x 30.4375
- Actual dose intensity (mg/month) = 30.4375 x Actual total dose exposed (mg) ÷ [(Date of last dose, zero or non-zero dose of study drug) – (Date of first non-zero dose of study drug) + 1]
- Intended dose intensity (mg/month) = 30.4375 x Total dose intended (mg) ÷ [(Date of last dose, zero or non-zero dose of study drug) – (Date of first non-zero dose of study drug) + 1]
- Relative dose intensity (RDI) (%) is the percentage of the actual dose intensity delivered relative to the intended dose intensity through to study drug discontinuation. RDI (%) = (actual dose intensity) ÷ (intended dose intensity) x 100

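### SAP 8.2 overall compliance is the same number as the relative dose intensity in SAP 8.1, and the overall and IS compliance percentages cannot tell a directed hold from missed doses

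*SAP*

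**What the plan says.** SAP 8.1 builds RDI in three steps. It starts from "Actual dose intensity (mg/month) = 30.4375 x Actual total dose exposed (mg") and "Intended dose intensity (mg/month) = 30.4375 x Total dose intended (mg"), each divided by the same bracket: the days from the first non-zero dose to the last dose, zero or non-zero, inclusive. It then sets "RDI (%) = (actual dose intensity) ÷ (intended dose intensity) x 100".

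The intended dose is a rate times a duration. For the continuous schedule (CS), "Total dose intended for the CS is estimated to be 60 mg x Duration of exposure on the CS (months) x 30.4375"; for the IS, "Total dose intended for the IS is estimated to be (60 mg /4) x Duration of exposure on the IS (months) x 30.4375". CS duration runs from the first to the last non-zero CS dose. IS duration runs from the first non-zero IS dose to the last IS dose, zero or non-zero. Neither formula removes days on which drug was withheld.

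SAP 8.2 then gives three percentages: "Overall Compliance (%) = [total dose exposed (mg) / total dose intended (mg)] x 100", and the same ratio restricted to CS and to IS dosing.

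The protocol directs holds in several places, including Table 4 for toxicity and CMV, and Section 5.6 for COVID-19. Section 5.1 says that interruption for adverse reactions "is allowed for up to 6 continuous weeks from drug interruption". Section 5.3.1 adds: "All treatment interruptions (including any missed doses, treatment delays) and discontinuations and their reasons are to be recorded" in the eCRF. Sections 9.9 and 9.10 provide a daily diary, with diary review and drug accountability at dispensing visits. SAP 8.1 also plans counts of subjects with missed doses by reason and, separately, of subjects whose dosing was interrupted for an adverse event or progression.

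**The concern.** RDI and compliance usually answer different questions. RDI shows how much of the planned dose was delivered, whatever the cause of any shortfall. Compliance shows whether subjects took what they were told to take. If both come from the same ratio, the second question has no percentage of its own. A figure below 100% could reflect poor adherence to an oral schedule of 7 days on and 21 days off, or correct handling of toxicity, and the percentage cannot show which. A reader of the study report would probably take a line labelled compliance as evidence about adherence.

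**Working it through.** The plan states no value for compliance or RDI, so there is no figure to reproduce. The check is algebra followed by an example.

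**1. Identity.** Let A be the actual total dose, I the total intended dose and D the day count in the SAP 8.1 bracket.

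- Actual dose intensity = 30.4375 × A / D
- Intended dose intensity = 30.4375 × I / D
- RDI = [(30.4375 × A / D) ÷ (30.4375 × I / D)] × 100 = A / I × 100
- Overall compliance (SAP 8.2) = A / I × 100

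The two are equal for every subject, whatever values A, I and D take. The CS and IS compliance lines have no RDI counterpart, so the duplication covers the overall line only.

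**2. Six-cycle example (168 days).** Inputs are 60 mg per dosing day, daily dosing in Cycles 1-2 (56 days), and 7 dosing days per cycle in Cycles 3-6. Cycles 1-2 are counted at 60 mg/day and the 112 days of Cycles 3-6 at 60/4 = 15 mg/day.

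- Intended: 56 × 60 + 112 × 15 = 3,360 + 1,680 = 5,040 mg
- Taken with full dosing: 56 × 60 + 4 × 7 × 60 = 5,040 mg, so compliance is 100%

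Now let one IS block, in Cycle 4 or 5, be held on instruction while every other capsule is taken. The dose lost is 7 × 60 = 420 mg.

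- Overall compliance = RDI = 4,620 / 5,040 = 91.7%
- IS line = 1,260 / 1,680 = 75.0%

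A subject who forgets the same seven capsules gets the same figures. Measured against doses prescribed, the first subject is at 4,620 / 4,620 = 100% and the second at 4,620 / 5,040 = 91.7%.

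**3. Where the hold does not count.** Protocol 5.3.1 has interrupted treatment resume on the IS. Suppose the 28 doses of Cycle 2 are held and IS dosing starts at Cycle 3. CS duration ends at the last non-zero CS dose and IS duration starts at the first non-zero IS dose, so the hold falls in neither.

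- Intended: 28 × 60 + 112 × 15 = 3,360 mg
- Taken: 28 × 60 + 4 × 420 = 3,360 mg, which is 100%

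SAP 8.1 also allows CS dates to be derived from the switching date. If that puts the held days back into CS exposure, the result is 3,360 / 5,040 = 66.7%. The text does not settle which reading applies. For the same reason, a held first IS block (Cycle 3) drops out of IS duration, which is why the example uses Cycle 4 or 5.

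**4. Sensitivity to how Cycles 1-2 are classed.** If they count as IS exposure at 15 mg/day, intended dose is 168 × 15 = 2,520 mg. Full dosing then reads 200% and one held block 4,620 / 2,520 = 183.3%. The hold still lowers the score, and RDI still equals compliance.

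**The case against.** The strongest reply is that adherence is in fact observed. Diaries are reviewed, returned capsules are counted, and reasons for missed doses are recorded. SAP 8.1 tabulates missed doses by reason separately from interruptions for adverse events or progression. A reader might infer from the identity that adherence is never measured, and the documents do not support that. What stands against the reply is that those summaries count subjects. None gives the proportion of prescribed doses taken, and SAP 8.2 uses none of the diary, capsule-count or reason data to separate directed holds.

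A second reply is that a large shortfall from a hold in the daily phase, such as 66.7%, does not follow from the SAP formulas on their plain reading. That is right (step 3 of the working). The effect is secure only for holds inside the IS interval.

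A reader might also connect the percentage to non-compliance as a reason for stopping drug in Protocol 5.7. Nothing links them: no threshold is given, and the percentage is an analysis quantity. The per-protocol population in SAP 4.5 turns on major deviations and makes no reference to it.

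Finally, the documents do not themselves define compliance as doses taken over doses prescribed, so the wish for that denominator is a judgement about what the label should mean. That is fair, but reporting one quantity under two names is hard to defend on any definition.

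**Conclusion.** The point holds in this form. Overall compliance and RDI are identical for every subject, without any assumption beyond reading total dose exposed in 8.2 as the actual total dose exposed of 8.1. The overall and IS compliance percentages do not separate a directed hold within the dosing interval from missed doses. In the six-cycle example the cost to a fully adherent subject is 8.3 percentage points overall (100 − 91.7) and 25 points on the IS line (100 − 75.0). Those sizes assume that Cycles 1-2 are counted at 60 mg/day, that all 112 days of Cycles 3-6 count as IS exposure, and that the held block is not the first IS block. Whether the CS line is affected depends on how the switching date is applied.

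The consequence is limited to descriptive exposure reporting. The ORR analysis and the discontinuation criteria are untouched. How Cycles 1-2 should be classed is a separate matter that also needs settling in SAP 8.1.

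**What to change.** Leave RDI as actual dose over the full planned dose. In SAP 8.2, redefine the denominator for the overall, CS and IS lines as planned dose minus the doses scheduled on days that the eCRF records as an investigator-directed or protocol-directed interruption. Two details should be written into the definition:

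- Deduct scheduled dosing days only. One held IS block removes 7 × 60 = 420 mg, giving 4,620 / 4,620 = 100% overall and 1,260 / (1,680 − 420) = 100% on the IS line.
- Deduct only days inside the interval that generated the intended dose. In step 3 of the working, removing the 28 held doses from a denominator that already omits them would give 3,360 / (3,360 − 1,680) = 200%.

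The cost is one SAP definition and a modest programming change, using interruption reasons that the protocol already requires in the eCRF. The small downside is that the result depends on those reasons being coded correctly.

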### **8.3. Adverse Events and Adverse Events of Special Interest**

Adverse events (AEs) will be captured from the first dose of study drug and continue until 30 days after the last dose of study drug. All AEs will be classified to SOC and PT by MedDRA Version 21.1 or later.

The Investigator will assess AEs for severity and relationship to study drug and determine if an AE meets the criteria for a SAE. The relationship of an AE to study drug is to be classified as ‘Related’, ‘Possibly Related’, or ‘Not Related’ by investigators. The study drug related AEs include both ‘Related’ and ‘Possibly Related’ AEs. Each AE will be graded using National Cancer Institute Common Terminology Criteria for Adverse Events (NCI CTCAE) v5.0. For the purpose of the summaries, AEs with missing relatedness will be considered to be related ME-401. AEs with missing severity (CTCAE grade) will be considered grade 3 (severe).

All AE listings will include the date of onset, date of resolution (if AE is resolved) and investigator’s assessment of severity and relationship to study drug. Missing (partial) start/stop dates will appear as missing (partial) in the subject data listings, but will be imputed to permit proper tabulation of AE data (See [Section 5.3.1](#)).

AEs will be summarized descriptively by number and percentage (%) of subjects with an event (n (%)), and number of events [e], by MedDRA SOC/PT and CTCAE grade.

A subject will be counted once at the SOC level and once at PT level. For summaries by SOC, PT, and intensity, a subject will be counted only at the maximum intensity level. Summaries by relatedness would be handled similarly to the summaries by intensity. Summaries by SOC and PT will be ordered by overall descending frequency of SOC and then, within a SOC, by overall descending frequency of PT. Summaries of PT will be ordered in descending frequency of PT.

#### **8.3.1. Treatment-Emergent Adverse Event (TEAE)**

TEAE is any new or worsening AE that started after the first dose of study drug until 30 days after the last dose of study drug. Treatment emergence will be determined by comparing the AE onset date with first dose date. If AE onset date is incomplete, treatment emergence will be imputed according to the algorithm in [Section 5.3.1](#). In general, only TEAEs will be included in the AE summaries but all AEs will be included in the listings.

#### **8.3.2. Adverse Events of Special Interest (AESI)**

AESIs are events of scientific and medical interest specific to the further understanding of the ME-401 safety profile. For ME-401, AESIs will comprise of (see study protocol [Section 5.3.2](#)):

- Cutaneous reactions, including skin rash Grade  $\geq 2$
- Oral mucositis or stomatitis Grade  $\geq 2$
- Diarrhea/colitis Grade  $\geq 2$
- AST/ALT Grade  $\geq 2$
- Non-infectious pneumonitis (NIP) of any grade
- Lung infection/pneumonia Grade  $\geq 2$
- Cardiomyopathy of any grade

AESI will be summarized by selected subgroups.

### **8.3.3. Summaries of Incidence of Adverse Events**

The number and percentage of subjects reporting TEAEs and AESIs will be summarized as below:

- Overall summary of TEAEs and AESIs
- TEAEs by SOC and PT
- TEAEs by PT
- TEAEs of Grade 3 and above by PT
- TEAEs by maximum grade and PT
- TEAEs leading to treatment discontinuation by PT
- TEAEs related to ME-401 leading to treatment discontinuation by PT
- TEAEs leading to treatment interruption by PT
- TEAEs related to study drug by PT
- AEs leading to death by PT
- Treatment-related AEs leading to death by PT
- Treatment-Emergent SAEs by SOC and PT
- Treatment-Emergent SAEs by PT
- Treatment-Emergent SAEs by maximum grade and PT
- Treatment-emergent AESIs by AESI Type and PT
- Treatment-emergent Grade 3 and Above AESIs by AESI type and PT
- Covid-19 events by grade
- Other important safety events including opportunistic infection, CMV infection, PJP infection, and fungal infection, cytopenia event, pulmonary event by maximum grade and PT

Selected analysis on TEAEs will be summarized by subgroups.

Listings will be produced for all AEs, TEAEs, SAEs, AEs leading to treatment discontinuation, AEs leading to death, AESI, and for subjects with grade 3 and above AEs.

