### 11.2.2. Statistical Analyses

The primary analysis of ORR for FL will be triggered after all 91 subjects in the PEP enrolled in the study (except those who discontinue early) have been followed for at least 6 months from the start of study drug.

The final analysis of DOR for FL will be triggered after most responders in the Primary Efficacy Population have a minimum of 12 months of follow-up from first response.

The final analysis of ORR and DOR for MZL will be triggered after most of the responders in the MZL ITT population (except those who discontinue early) have been followed for at least 12 months from first response.

Summary statistics for continuous variables will include the mean, standard deviation, median, and range (minimum/maximum). Categorical variables will be presented as frequency counts and percentages. Time-to-event variables will be summarized using Kaplan-Meier (KM) methods (median, 95% CI, number of events, number censored, KM figures). Data listings will be created to support each table and to present all data.

The efficacy analysis of ORR for MZL as determined by the IRRC will be based on the ITT MZL Population, utilizing the best overall ORR prior to first PD. The CR rate as determined by the IRRC will be reported similarly. The ORR as determined by the IRRC in the EE Population will be reported as a sensitivity analysis.

Secondary efficacy endpoints including DOR, DORR, PFS, TTF, time to recapture of response (as assessed by the IRRC and/or Investigator); and overall survival (OS) will be summarized using KM summary statistics for the ITT IS FL Population and ITT MZL Population respectively.

Similarly, the efficacy endpoints based on Investigator assessments will be summarized as supportive analyses.

Safety analyses will be performed on the Safety Population, as defined in [Section 11.2.1](#).

Overall summary of safety will include but not limited to the following analyses:

- TEAEs, including severity and possible relationship to study drug and/or study treatment
- AESIs
- treatment-emergent SAEs
- discontinuations from study treatment due to AEs
- treatment-emergent abnormal changes in laboratory values
- treatment-emergent abnormal changes in vital signs.

The rate of AESIs and the respective 95% CI will be calculated by dosing group (CS and IS) and overall.

Time to AESIs will be calculated from the first day of study treatment to first occurrence of AESI, utilizing KM methodology.

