Safety variables including TEAEs, AESIs, laboratory tests, vital signs, and ECGs will be summarized descriptively.

Further safety and efficacy analyses, handling of missing information, and subset analyses will be detailed in the study SAP.

Population PK analyses will be described in the Population PK Analysis Plan.

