## 2.4. Determination of Sample Size

### Sample Size for FL

The study will test the null hypothesis that the IRRC-reviewed ORR is  $\leq 48\%$  against the alternative hypothesis that it is  $\geq 65.5\%$ . The sample size for the primary efficacy population for FL is estimated to be 91 subjects, with at least 90% power and 1-sided alpha = 0.025.

Safety analysis will be performed based on the Safety Population, with analysis focused on the IS FL subjects at the primary analysis database lock for FL submissions. With a total sample size of 120 FL subjects treated with ME-401 IS dosing regimen, if  $\leq 15$  subjects experience Grade  $\geq 3$  AESIs (i.e., subject incidence rate of  $\leq 12.5\%$  with 95% CI of 7.2–19.8%), the study can rule out the possibility of having an incidence rate  $\geq 20\%$  for Grade  $\geq 3$  AESIs with the IS dosing regimen. In addition, with a total sample size of 120 FL subjects, if  $\leq 5$  subjects experience a particular type of events (i.e., subject incidence rate of  $\leq 4.2\%$  with 95% CI 1.4–9.5%), the study can rule out the possibility of having an incidence rate of  $\geq 10\%$  for this AE.

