### **3.3.2. Incidence Rate of Adverse Event of Special Interests (AESIs)**

The rate of AESIs is calculated as the proportion of subjects with at least one AESI.

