## **10. CHANGES FROM ANALYSIS PLANNED IN PROTOCOL**

No changes from planned analysis in protocol.

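### The SAP plans AESI incidence as number and percentage only, while the current protocol asks for a 95% CI, and the SAP's pooled safety counts do not fit the number enrolled

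*SAP*

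**What the plan says.** **Protocol.** Section 11.2.2 is specific: "The rate of AESIs and the respective 95% CI will be calculated by dosing group (CS and IS) and overall". Shortly afterwards the same section says more generally: "Safety variables including TEAEs, AESIs, laboratory tests, vital signs, and ECGs will be summarized descriptively".

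**SAP, incidence.** Section 3.3.2 defines the endpoint as a bare proportion: "The rate of AESIs is calculated as the proportion of subjects with at least one AESI". Section 8.3 sets the summary statistics for all AEs as subject counts, percentages and event counts. Section 8.3.3 introduces its list of tables with "The number and percentage of subjects reporting TEAEs and AESIs will be summarized as below"; one of them is "Treatment-emergent Grade 3 and Above AESIs by AESI type and PT". The only intervals in the AESI sections are in 8.3.4, for median time to AESI and median follow-up. For other proportions the SAP does name a method: two-sided 95% exact Clopper-Pearson for ORR (7.1), CR rate (7.2.3) and recapture rate (7.2.6).

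**SAP, changes.** Section 10 states: "No changes from planned analysis in protocol".

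**Sample size.** Protocol 11.1 and SAP 2.4 say that with 120 FL subjects on IS and at most 15 having a Grade 3 or higher AESI (12.5%, 95% CI 7.2–19.8%), "the study can rule out the possibility of having an incidence rate" of 20% or more. At most 5 of 120 with a particular AE (CI 1.4–9.5%) likewise excludes 10%. SAP 2.4 adds pooled FL and MZL versions at 184 subjects: at most 25 (CI 9.0–19.4%) for 20%, and at most 9 (CI 2.3–9.1%) for 10%.

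**Enrolment.** Protocol 8.3 reports 121 FL and 32 MZL subjects treated on IS, with enrolment closed.

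**The concern.** The protocol names an interval for AESI incidence, and the SAP, which governs what is programmed, does not produce it and gives no method for it. A programmer following the SAP would deliver percentages without limits.

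This matters mainly because the safety argument in the sample-size section is an argument about an upper confidence limit. It concerns any-type Grade 3 or higher AESIs in IS subjects. The protocol's CI sentence covers AESIs as defined in Protocol 5.3.2, which are mostly Grade 2 or higher and for some types any grade. So carrying that sentence into the SAP word for word would still leave the Grade 3 or higher interval unplanned.

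The pooled statement raises a second problem. It was written for 184 subjects (120 + 64). MZL enrolment closed at 32 of 64, so a reader who applies the printed counts to the final tables could claim more precision than the data give.

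**Working it through.** **Inputs.** Counts, denominators and stated CIs from SAP 2.4 (the FL figures are also in Protocol 11.1). IS enrolment from Protocol 8.3: 121 + 32 = 153.

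**Formula.** Two-sided 95% exact (Clopper-Pearson) limits for x of n:
- lower = 0.025 quantile of Beta(x, n − x + 1)
- upper = 0.975 quantile of Beta(x + 1, n − x)

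**Step 1. Reproduce the plan's figures.**

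| x/n | Rate | Exact 95% CI | Stated CI |
|---|---|---|---|
| 15/120 | 12.5% | 7.17–19.78% | 7.2–19.8% |
| 5/120 | 4.2% | 1.37–9.46% | 1.4–9.5% |
| 25/184 | 13.6% | 8.99–19.40% | 9.0–19.4% |
| 9/184 | 4.9% | 2.26–9.08% | 2.3–9.1% |

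All four agree. For 15/120 the Wald interval (6.58–18.42%) and the Wilson interval (7.72–19.60%) do not match, so the planning was done with the exact method. As a cross-check, P(X ≤ 15 | n = 120, p = 0.20) = 0.0218 and P(X ≤ 16) = 0.0388. Fifteen is therefore the correct cut-off at one-sided 0.025.

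**Step 2. Does the method need naming?** At 16/120 (13.3%) the upper limit is 20.75% exact, 20.56% Wilson and 19.42% Wald. Next to the cut-off, Wald would exclude 20% and the other two would not.

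**Step 3. FL at the enrolled number.** 15/121 gives 7.11–19.62% and 16/121 gives 7.75–20.58%. The cut-off for 20% stays at 15. For 10%, 5/121 has an upper limit of 9.38% and 6/121 of 10.48%, so it stays at 5.

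**Step 4. Pooled IS at the enrolled number.**

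| x/n | Rate | Exact 95% CI | Reference rate | Excluded? |
|---|---|---|---|---|
| 25/153 | 16.3% | 10.86–23.17% | 20% | No |
| 21/153 | 13.7% | 8.70–20.21% | 20% | No |
| 20/153 | 13.1% | 8.17–19.46% | 20% | Yes |
| 9/153 | 5.9% | 2.72–10.87% | 10% | No |
| 8/153 | 5.2% | 2.28–10.04% | 10% | No |
| 7/153 | 4.6% | 1.86–9.20% | 10% | Yes |

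The SAP's pooled counts of 25 and 9 would have to read 20 and 7.

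**The case against.** A reader might infer that the trial has a stated safety test which the SAP leaves without an analysis. The documents do not support that, for three reasons.

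- The 20% and 10% figures appear only in the sample-size sections, as conditional precision statements. No safety hypothesis, alpha or decision rule is attached to them, unlike the ORR hypotheses in the same sections.
- Grade 3 or higher AESIs are analysed. SAP 8.3.3 tabulates them by type and preferred term, and 8.3.4 plans Kaplan-Meier estimates of time to the first one.
- The percentages do not stand alone. Tables carry the count and the column N, with separate FL, MZL and all-IS columns, so anyone can compute an exact interval from a reported count and denominator.

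It is also tempting to say that the SAP removed the interval and then wrongly denied any change. That cannot be shown. SAP v3.0 (June 2021) was updated to Amendment 4, whereas the protocol supplied formalises Amendment 5, and the Amendment 4 wording is not available. The same timing explains the outdated 184: MZL enrolment closed in August 2022, after the SAP was written. Finally, the FL count of 15 is unchanged at 121, so the main precision statement is intact.

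All of this stands, and it limits the point to a mismatch between the current texts. It does not remove the mismatch. The protocol's general line about descriptive summaries does not cancel its specific request for a CI, because an interval is itself compatible with descriptive reporting.

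**Conclusion.** The point holds as an alignment gap. The current protocol requires a 95% CI for the AESI rate; the SAP plans none and names no method. Neither document explicitly plans an interval for the any-type Grade 3 or higher AESI rate in IS subjects, on which the precision statement relies. The SAP's pooled counts overstate what 153 subjects can exclude, by 5 subjects for 20% (25 against 20) and by 2 for 10% (9 against 7). The FL counts are unaffected.

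No planned decision changes, and the missing intervals can be computed from counts and denominators. The conclusion assumes the exact method, which reproduces every stated interval, and takes the IS totals in Protocol 8.3 as the safety denominators. If the number in a given data cut differs, the cut-offs must be recomputed.

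**What to change.** - **SAP 8.3.3:** add two-sided 95% exact Clopper-Pearson CIs for the proportion of subjects with any AESI and with any Grade 3 or higher AESI, for CS, IS FL, IS Total and overall. SAP Table 4 lists IS FL, IS MZL, IS Total and CS for safety, so the overall column is new. Intervals for IS MZL and for individual AESI types are optional; the protocol does not ask for them.
- **SAP 2.4:** restate the pooled precision statement at the number actually dosed (at 153: 20 for the 20% figure, 7 for the 10% figure). Keep it as a descriptive statement of precision and add no decision rule.
- **SAP 10:** check the no-changes statement against the current protocol when the SAP is next updated.

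The cost is SAP wording plus an interval and one overall column in existing tables, with no new data. The downside is wide intervals in small groups: 4/32 in MZL, for example, would be 12.5% with a CI of 3.5–29.0%.
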